### **8.1.5.2 Clinical Laboratory Data**

Clinical laboratory test values will be summarized by treatment group at each visit during the DB Treatment Period and separately for subjects treated in the OL Treatment Period. The baseline value will be the last measurement on or before the day of the first dose of double-blind study drug. This same baseline value will be used for all summary tables in the DB, OL, and Post-Treatment Periods.

Change from baseline to each post-baseline visit, including Final DB and OL Treatment Visits and applicable post-treatment visits, will be summarized for each protocol-specified laboratory parameter by treatment group; the baseline and visit means will be calculated along with the mean, standard deviation, and median for the change from baseline. The differences between the active and placebo arms in the DB Treatment Period will be analyzed using an ANOVA model with treatment arm as the factor. Separate tables will be used to summarize the changes from baseline to the DB Treatment Period visits (Arms A and B), the OL Treatment Period visits (Arm B), and the Post-Treatment Period visits (Arms A and B).

During the DB and OL Treatment periods, laboratory test values will be categorized as low, normal, or high based on reference ranges of the laboratory used in this study. Shift tables from baseline to minimum value and from baseline to maximum value during the DB and OL Treatment periods will be created. The shift tables will cross-tabulate, by treatment arm, the frequency of subjects with baseline values below/within/above the normal range versus minimum/maximum values below/within/above the normal range.

In addition, the number and percentage of subjects with post-baseline values during the DB and OL Treatment periods meeting pre-specified criteria for potentially clinically significant laboratory values or toxicity grades will be presented by treatment arm. Comparisons between arms will be performed on the percentage of subjects with laboratory abnormalities (by potentially clinically significant criterion or toxicity grade) during the DB Treatment Period for each parameter using Fisher's exact tests.

### **8.1.5.3 HIV-1 RNA Data**

For the HCV/HIV co-infected subjects who were on stable HIV-1 ART at initiation of double-blind study drug, the numbers and percentages of subjects with 2 consecutive HIV-1 RNA values  $\geq 200$  copies/mL during the DB and OL Treatment Periods will be calculated for each treatment arm.

### **8.1.5.4 Vital Signs Data**

Vital signs will be summarized by treatment group (DB active and DB placebo) at each visit during the DB Treatment Period and separately for subjects treated in the OL Treatment Period. The baseline value will be the last measurement on or before the day of the first dose of double-blind study drug. This same baseline value will be used for all summary tables in the DB, OL, and Post-Treatment Periods.

Mean changes in temperature, systolic and diastolic blood pressure, pulse, and weight from baseline to each post-baseline visit, including Final DB and OL Treatment Visits, will be summarized descriptively by arm. The differences between the active and placebo arms in the DB Treatment Period will be analyzed using contrasts within an ANOVA model with treatment arm as the factor. Frequencies and percentages of subjects with post-baseline values meeting pre-defined criteria for potentially clinically significant vital sign values will be summarized by treatment arm, separately for the DB and OL Treatment Periods. Comparisons between arms will be performed on the percentage of subjects experiencing a value meeting the criteria during the DB Treatment Period for each parameter using Fisher's exact tests.

### **8.1.6 Pharmacokinetic and Exposure-Response Analyses**

Plasma concentrations of ABT-530 and ABT-493 and possible metabolites and pharmacokinetic parameter values for ABT-493 and ABT-530 will be tabulated for each subject and group. Summary statistics will be computed for each time and visit.

Plasma concentration data from this study may be combined with data from other studies and analyzed using the following general methodology:

Population pharmacokinetic analyses will be performed using the actual sampling time relative to dosing. Pharmacokinetic models will be built using a non-linear mixed-effect modeling approach with the NONMEM software (version VII, or higher version). The structure of the starting pharmacokinetic model will be based on the pharmacokinetic analysis of data from previous studies. Apparent oral clearance (CL/F) and apparent volume of distribution (V/F) of the PK analytes will be the pharmacokinetic parameters of major interest in the NONMEM analyses. If necessary, other parameters, including the parameters describing absorption characteristics, may be fixed if useful in the analysis. The evaluation criteria described below will be used to examine the performance of different models.

- The objective function of the best model is significantly smaller than the alternative model(s).
- The observed and predicted concentrations from the preferred model are more randomly distributed across the line of unity (a straight line with zero intercept and a slope of one) than the alternative model(s).
- Visual inspection of model fits, standard errors of model parameters and change in inter-subject and intra-subject error.

Once an appropriate base pharmacokinetic model (including inter- and intra-subject error structure) is developed, empirical Bayesian estimates of individual model parameters will be calculated by the posterior conditional estimation technique using NONMEM. The relationship between these conditional estimates CL/F and V/F values with only potentially physiologically relevant or clinically meaningful covariates (such as subject age, sex, body weight, concomitant medications, laboratory markers of hepatic or renal function, etc.) will be explored using either stepwise forward selection method, or generalized additive method (GAM) or another suitable regression/smoothing method at a significance level of 0.05. After identification of all relevant covariates, a stepwise backward elimination of covariates from the full model will be employed to evaluate the

significance (at  $P < 0.005$ , corresponding to an increase in objective function  $> 7.88$  for one degree of freedom) of each covariate in the full model.

In general, all continuous covariates will be entered in the model, initially in a linear fashion, with continuous covariates centered around the median value. Linear or non-linear relationships of primary pharmacokinetic parameters with various covariates may also be explored. For example:

$$TVCL_i = \text{Theta}(1) + \text{Theta}(2) (\text{Comedication } [1,2,\dots]) + \text{Theta}(3) (\text{WT}_i - \text{median value}) + \text{Theta}(4) (\text{AGE}_i - \text{median value}).$$

Where  $TVCL_i$  = Typical value of clearance for an individual,  $\text{Theta}(1)$  is the intercept and  $\text{Theta}(2) - (4)$  are regression parameters relating the fixed effects (weight and age centered on the median value) to clearance.

Relationship between exposure and clinical observations (antiviral activity) will be explored. Exposure-response relationships for primary and secondary efficacy variables and/or some safety measures of interest may also be explored.

The relationship between exposure (e.g., population pharmacokinetic model predicted concentrations over time or average concentrations or AUC or trough concentrations of the individual model-predicted pharmacokinetic profiles, or some other appropriate measure of exposure) and antiviral activity will be explored.

Logistic regression analyses will explore the relationship between exposure and one or more virologic endpoints (e.g.,  $SVR_{12}$ , relapse following end of treatment and breakthrough on treatment).

Additionally, relationship between exposure and safety endpoints of interest may also be explored. Additional analyses will be performed if useful and appropriate.

## 8.2 Determination of Sample Size

It is planned to enroll a total of approximately 504 subjects. In China, approximately 150 GT1-infected subjects will be randomized to receive active treatment (Arm A) or placebo (Arm B) in a 2:1 ratio; approximately 150 GT2-infected subjects will be randomized in a 2:1 ratio; and approximately 60 GT3, 4, 5, or 6-infected subjects will be randomized in a 2:1 ratio. Across Singapore and South Korea, approximately 105 GT1-infected subjects and approximately 39 GT2-infected subjects will be randomized to Arm A and Arm B; randomization will occur within each regional country in a 2:1 ratio. A maximum of 50 of the 504 subjects will have HCV/HIV co-infection. The expected approximate number of subjects by subpopulation is presented in [Table 9](#).

For the first primary endpoint, with a sample size of 336 GT1 – 6-infected subjects in the active treatment arm (Arm A) and assuming that 97% of these subjects will achieve SVR12, this study has greater than 95% power to show non-inferiority to a historical control regimen, using a threshold of 90%, based on a 1-sample test for superiority using EAST 6.3. The threshold of 90% was based on a historical SVR12 rate of 96% and a 6% non-inferiority margin. To establish efficacy, the lower bound of a 2-sided 95% CI for the SVR12 rate must be greater than 90% (based on a normal approximation of a single binomial proportion CI). No adjustment for dropouts is applicable because subjects who do not have data at Post Treatment Week 12 (after imputing) are counted as failures for SVR12.

For the second primary endpoint, with a sample size of 170 GT1-infected subjects in the active treatment arm (Arm A) and assuming that 97% of these subjects will achieve SVR12, this study has 90% power to show non-inferiority to a historical control regimen, using a threshold of 91%, based on a 1-sample test for superiority using EAST 6.3. The threshold of 91% was based on a historical SVR12 rate of 97% and a 6% non-inferiority margin. To establish efficacy, the lower bound of a 2-sided 95% CI for the SVR12 rate must be greater than 91% (based on a normal approximation of a single binomial proportion CI). No adjustment for dropouts is applicable because subjects who do not have data at Post Treatment Week 12 (after imputing) are counted as failures for SVR12.

For the third primary endpoint, with a sample size of 126 GT2-infected subjects in the active treatment arm (Arm A) and assuming that 96% of these subjects will achieve SVR12, this study has greater than 80% power to show non-inferiority to a historical control regimen, using a threshold of 89%, based on a 1-sample test for superiority using EAST 6.3. The threshold of 89% was based on a historical SVR12 rate of 95% and a 6% non-inferiority margin. To establish efficacy, the lower bound of a 2-sided 95% CI for the SVR12 rate must be greater than 89% (based on a normal approximation of a single binomial proportion CI). No adjustment for dropouts is applicable because subjects who do not have data at Post Treatment Week 12 (after imputing) are counted as failures for SVR12.

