## **8.0 Statistical Methods and Determination of Sample Size**

### **8.1 Statistical and Analytical Plans**

The primary analysis will occur after all subjects in Arm A have completed the PT Week 12 Visit or prematurely discontinued the study. The primary analysis will summarize data through PT Week 12 for Arm A subjects and data through the DB Treatment Period for Arm B subjects. The data for the primary analysis will be locked after data cleaning, and data collected after this lock will be added to a new version of the database. Results from the primary analysis will be described in the primary clinical study report (CSR) and submitted to regulatory agencies as part of an NDA submission. An interim analysis will occur after all Arm A subjects have completed the PT Week 24 Visit or prematurely discontinued the study and all Arm B subjects have completed the PT

Week 12 Visit or prematurely discontinued the study. The data for the interim analysis will be locked after data cleaning. Data collected after this lock will be added to a new version of the database which will be cleaned and locked at the end of the study.

SAS® (SAS Institute, Inc., Cary, NC) for the UNIX operating system will be used for all analyses. All statistical tests and confidence intervals will be two-sided with an alpha level of 0.05. Descriptive statistics will be provided, such as the number of observations (N), mean, and standard deviation (SD) for continuous variables and counts and percentages for categorical variables.

Analyses will be performed on the intent-to-treat (ITT) population defined as all randomized subjects who receive at least one dose of study drug in the DB Treatment Period, unless otherwise specified. The primary and secondary efficacy endpoints will be analyzed on the ITT population treated with active study drug in the DB Treatment Period (Arm A). Sensitivity analyses of the primary efficacy endpoint, when applicable, will be performed on the ITT population modified to exclude subjects of multiple GTs according to the central laboratory or phylogenetic analyses (mITT-GT), and on the mITT-GT population modified to exclude subjects who did not achieve SVR12 for reasons other than virologic failure (mITT-GT-VF). In addition, some analyses will be performed on the OL Population defined as all subjects who receive at least one dose of study drug during the OL Treatment Period.

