For the third primary endpoint, with a sample size of 126 GT2-infected subjects in the active treatment arm (Arm A) and assuming that 96% of these subjects will achieve SVR₁₂, this study has greater than 80% power to show non-inferiority to a historical control regimen, using a threshold of 89%, based on a 1-sample test for superiority using EAST 6.3. The threshold of 89% was based on a historical SVR₁₂ rate of 95% and a 6% non-inferiority margin (see Section 4.3.1). To establish efficacy, the lower bound of a 2-sided 95% CI for the SVR₁₂ rate must be greater than 89% (based on a normal approximation of a single binomial proportion CI). No adjustment for dropouts is applicable because subjects who do not have data at PT Week 12 (after imputing) are counted as failures for SVR₁₂.

Table 1. Summary of Approximate Subject Numbers Expected by Subpopulation

Sub-Population	DB Active	DB Placebo	Total
GT1	170	85	255
China	100	50	150
HCV/HIV Co-infected	10	5	15
Not HCV/HIV Co-infected	90	45	135
Asian Regional Countries	70	35	105
HCV/HIV Co-infected	6	3	9
Not HCV/HIV Co-infected	64	32	96
GT2	126	63	189
China	100	50	150
HCV/HIV Co-infected	10	5	15
Not HCV/HIV Co-infected	90	45	135
Asian Regional Countries	26	13	39
HCV/HIV Co-infected	2	1	3
Not HCV/HIV Co-infected	24	12	36
GT3 – 6	40	20	60
China	40	20	60
HCV/HIV Co-infected	4	2	6
Not HCV/HIV Co-infected	36	18	54
Total GT1 – 6	336	168	504
China	240	120	360
HCV/HIV Co-infected	24	12	36
Not HCV/HIV Co-infected	216	108	324
Asian Regional Countries	96	48	144
HCV/HIV Co-infected	8	4	12
Not HCV/HIV Co-infected	88	44	132

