10.2 Handling of Multiplicity

In order to control the Type I error rate at 0.05, a fixed sequence testing procedure⁷ will be used for the ranked primary efficacy endpoints. That is, only if success has been demonstrated for the first primary endpoint will the testing proceed to the second primary endpoint. Similarly, only if success has been demonstrated for the second primary endpoint will the testing proceed to the third primary endpoint.

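### The 90% power stated for the GT1 primary endpoint is not the power of the confidence-bound rule that decides success; under that rule it is about 97%, and no fixed-sequence power is given.

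*Protocol*

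**What the plan says.** Protocol 8.2 sizes each primary endpoint separately.

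- **GT1:** the inputs are "with a sample size of 170 GT1-infected subjects in the active treatment arm (Arm A) and assuming that 97% of these subjects" will respond, and the claim is that "this study has 90% power to show non-inferiority to a historical control regimen, using a threshold of 91%, based on a 1-sample test for superiority", computed in EAST 6.3. The same paragraph then sets the success criterion: "the lower bound of a 2-sided 95% CI for the SVR 12 rate must be greater than 91% (based on a normal approximation" to a single binomial proportion).
- **GT2:** the inputs are "with a sample size of 126 GT2-infected subjects in the active treatment arm (Arm A) and assuming that 96% of these subjects" will respond, and "this study has greater than 80% power to show non-inferiority to a historical control regimen, using a threshold of 89"%. SAP 4.3 repeats this ("this study has greater than 80% power to show non-inferiority to a historical" control).
- **Combined GT1 to GT6:** 336 subjects, 97% assumed, 90% threshold, power above 95%.

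Protocol 8.1.2.1 and SAP 10.3 confirm the deciding rule: a normal-approximation interval, with Wilson's method only if the observed rate is 100%. Protocol 8.1 states that "All statistical tests and confidence intervals will be two-sided with an alpha level of 0.05". The endpoints are tested in a fixed order. Under SAP 10.2, "only if success has been demonstrated for the second primary endpoint will the testing proceed to the third primary endpoint", and the second is likewise tested only after the first succeeds. The sample-size text gives no power for the sequence.

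**The concern.** Each paragraph takes its power from one procedure and its success criterion from another. A one-sample test that uses the variance at the threshold and a confidence bound that uses the variance at the observed rate need different numbers of responders. Close to 100% response the difference is large enough to change the power. The stated power is the plan's justification for 170 GT1 and 126 GT2 active subjects, so it should describe the rule that will be applied. GT2 can be won only if the combined and GT1 endpoints have been won, so a per-endpoint figure is also not the chance that GT2 succeeds.

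**Working it through.** **Inputs** (Protocol 8.2, repeated in SAP 4.3): combined n = 336, threshold p0 = 0.90, assumed p1 = 0.97; GT1 n = 170, p0 = 0.91, p1 = 0.97; GT2 n = 126, p0 = 0.89, p1 = 0.96. Two-sided alpha is 0.05, so z = 1.96. Missing outcomes count as failures, so there is no dropout adjustment.

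**Step 1: reproduce the printed figures.** A one-sample normal test with the variance at the threshold has power

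Φ{ [p1 − p0 − 1.96·√(p0(1−p0)/n)] / √(p1(1−p1)/n) }.

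- GT1: (0.06 − 1.96 × 0.02195) / 0.01308 = 1.298, so power is 90.3% (printed: 90%).
- GT2: (0.07 − 1.96 × 0.02787) / 0.01746 = 0.880, so power is 81.1% (printed: above 80%).

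Other forms tried for GT1 do not give 90%:

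| Form | GT1 power |
|---|---|
| Variance at the assumed rate | 99.6% |
| Arcsine | 92.6% |
| Threshold variance with continuity correction | 85.8% |
| Threshold variance throughout | 78.0% |
| Threshold variance in the critical value, one-sided 0.05 | 96.6% |

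For GT2, a figure above 80% also fits the arcsine form (86.6%) and the assumed-rate-variance form (98.0%), so the match identifies the method for GT1 only.

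**Step 2: find where the written rule passes.** Success requires p̂ − 1.96·√(p̂(1−p̂)/n) > p0.

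| Endpoint | Responders | p̂ | Lower bound | Threshold | Pass |
|---|---|---|---|---|---|
| Combined | 311/336 | 0.9256 | 0.8975 | 0.90 | no |
| Combined | 312/336 | 0.9286 | 0.9010 | 0.90 | yes |
| GT1 | 160/170 | 0.9412 | 0.9058 | 0.91 | no |
| GT1 | 161/170 | 0.9471 | 0.9134 | 0.91 | yes |
| GT2 | 117/126 | 0.9286 | 0.8836 | 0.89 | no |
| GT2 | 118/126 | 0.9365 | 0.8939 | 0.89 | yes |

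Every higher count also passes, including 100% with the Wilson bound.

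**Step 3: exact binomial power of that rule.**

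- Combined: P(X ≥ 312 | 336, 0.97) > 99.9%.
- GT1: P(X ≥ 161 | 170, 0.97) = 96.7%. The difference from the printed 90% is 6.7 points.
- GT2: P(X ≥ 118 | 126, 0.96) = 93.3%.

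The GT1 result does not depend on n being exactly 170. Repeating steps 2 and 3 for every N from 160 to 180 gives 94.2% to 98.0%.

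**Step 4: the fixed sequence.** GT1 (170 at 97%), GT2 (126 at 96%) and GT3 to GT6 (40 in Arm A) were treated as independent binomials and enumerated jointly. The GT3 to GT6 rate is an assumption, set at 96% and varied from 90% to 97%.

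- Combined and GT1 both succeed: 96.7% (96.4% to 96.7% over that range).
- All three succeed: 90.2% throughout.

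The combined endpoint costs almost nothing, so the result is close to 0.967 × 0.933 = 0.902. The sequence takes less than 0.1 point off GT1 (about 0.2 if the GT3 to GT6 rate is 90%) and about 3 points off GT2.

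**The case against.** The strongest reply is that nothing is at risk. The printed GT1 figure is lower than the true one, so the error is conservative. The other two statements are inequalities, and both hold under the written rule. The GT2 statement holds even after the fixed sequence is counted (90.2%). Each paragraph states power for its own endpoint and none claims joint power. The testing order is disclosed. The sizing test is named, and correcting the power text changes no analysis. The sample sizes are approximate, so counts and power to a decimal place could suggest more precision than the plan can have. All of this stands, and it limits the point to a correction of the power statement.

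It does not rescue the GT1 figure. A stated 90% is a value, not a lower limit, and the rule in the same paragraph does not have that power at 170 or at any N from 160 to 180.

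A reader might go further and infer that the trial is underpowered. Multiplying the two sizing-test values gives 0.903 × 0.811 = 73%, and a score (Wilson) bound at exactly 170 and 126 gives 85.9% for GT1, 75.9% for GT2 and 65.2% for all three. The documents do not support that reading. The plan decides on the Wald bound; it uses Wilson for the primary decision only at 100% response, and SAP 10.5 otherwise lists Wilson intervals for these endpoints as sensitivity analyses. The Wilson shortfall is also an accident of the exact N: one more subject gives 92.6% for GT1 (n = 171) and 86.2% for GT2 (n = 127).

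**Conclusion.** The point holds for GT1. The stated 90% is not the power of the plan's success rule, which is 96.7% at the planned N and assumed rate, so the documents understate it by about 7 points. The combined and GT2 statements are correct as inequalities (>99.9% and 93.3%). What is missing is the probability of winning GT2, and so all three endpoints, in the fixed order: about 90.2%.

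These figures rest on the plan's own sample sizes, rates and thresholds, on independence between genotype groups, and on an assumed GT3 to GT6 rate that hardly affects the result. That the 90% came from a threshold-variance test is inferred from the arithmetic, because the EAST option is not stated. The mismatch with the written rule does not depend on that inference. No shortfall in sample size is shown. This point concerns the power statement only; the error rate of the Wald bound at the threshold is a separate question.

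**What to change.** In Protocol 8.2 and SAP 4.3:

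- Replace the one-sample-test figures with the exact binomial power of the stated success rule at the planned N: combined >99.9%, GT1 about 97%, GT2 about 93%.
- Add the probability of winning all three endpoints in the fixed sequence, about 90%, with the assumed GT3 to GT6 rate.
- Give the minimum passing counts (312/336, 161/170, 118/126), labelled as illustrative at the planned N, since the analysed numbers may differ.

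The cost is a wording change to one section in each document and a short calculation. Enrolment, conduct and the analysis rule stay as they are.

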**Table 9. Summary of Approximate Subject Numbers Expected by Subpopulation**

Sub-Population	DB Active	DB Placebo	Total
GT1	170	85	255
China	100	50	150
HCV/HIV Co-infected	10	5	15
Not HCV/HIV Co-infected	90	45	135
Asian Regional Country(ies)	70	35	105
HCV/HIV Co-infected	6	3	9
Not HCV/HIV Co-infected	64	32	96
GT2	126	63	189
China	100	50	150
HCV/HIV Co-infected	10	5	15
Not HCV/HIV Co-infected	90	45	135
Asian Regional Country(ies)	26	13	39
HCV/HIV Co-infected	2	1	3
Not HCV/HIV Co-infected	24	12	36
GT3 – 6	40	20	60
China	40	20	60
HCV/HIV Co-infected	4	2	6
Not HCV/HIV Co-infected	36	18	54
Total GT1 – 6	336	168	504
China	240	120	360
HCV/HIV Co-infected	24	12	36
Not HCV/HIV Co-infected	216	108	324
Asian Regional Country(ies)	96	48	144
HCV/HIV Co-infected	8	4	12
Not HCV/HIV Co-infected	88	44	132

